11.5 Other Sensitivity Analysis

Other sensitivity analyses will be used to examine 2 different issues in this study:

- 1. Robustness of the key secondary efficacy analysis (MMRM) results for the CGI-I will be examined using the 2 sensitivity analysis models described in Section 11.4.
- 2. Impact of potential unblinding of 10 subjects due to unintentional urine drug screen performed erroneously after the final on-treatment assessments (see Section 18.1 for further details)

To evaluate whether the potential unblinding modified the efficacy results, sensitivity analyses of the primary efficacy (ADHD-RS-5 total score) and key secondary efficacy (CGI-I) analyses will be performed, in which these 10 subjects will be excluded from the FAS. The results between the primary and key secondary efficacy analyses and the sensitivity analyses will be examined.

11.6 Other Secondary Efficacy Endpoint(s) and Analysis

No other secondary efficacy endpoints are defined for this study.

11.7 Exploratory Efficacy Endpoint(s) and Analysis

The primary efficacy endpoint, change from baseline of the ADHD-RS-5 total score at Visit 6 (Week 4), will be analyzed separately for age group (6-8 years and 9-12 years), sex group (male and female), race group (white and non-white), and ethnicity group, using the same analysis method (MMRM) as for the primary efficacy endpoint, with treatment group, visit, age group (6-8 years vs. 9-12 years) and the interaction of treatment group with visit as factors, baseline ADHD-RS-5 total score as a covariate, and the interaction of baseline ADHD-RS-5 total score with visit adjusted in the model. The age group will not be included as a factor for the subgroup

analysis for age group. ADHD-RS subscales will also be analyzed separately for age group (6-8 years and 9-12 years) using a similar model as the primary efficacy endpoint.

Descriptive statistics will be displayed for each treatment group within each age group, sex group, race group, and ethnicity group as well as the least squares means and standard errors resulting from the MMRM. To compare SHP465 6.25 mg and placebo, the difference of least squares means and the corresponding 95% CI, and the effect size (defined as difference of the least squares means divided by the estimated SD from the unstructured covariance matrix) will be displayed. The effect size will only be presented for Visit 6 (Week 4). In addition, the ADHD-RS total score will be summarized at each visit by treatment group for each age group (6-8 years and 9-12 years), sex group (male and female), race group (white and non-white), and ethnicity group. ADHD-RS subscales will also be summarized at each visit by treatment group and age group (6-8 years and 9-12 years).

The key secondary efficacy endpoint, CGI-I score, will be analyzed separately for each age group (6-8 years and 9-12 years), sex group (male and female), race group (white and non-white), and ethnicity using the same analysis method (MMRM) as for the primary efficacy endpoint with treatment group, visit, and the interaction of treatment group with visit as factors, and baseline CGI-S score used as a covariate, and interaction of the baseline CGI-S score with the visit adjusted in the model.

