2.2 Randomization

Protocol SHP465-309

Shire

Subject numbers are assigned to all subjects as they consent to take part in the study. Within each site (numbered uniquely within a protocol), this number is assigned to subjects according to the sequence of presentation for study participation.

The actual treatment given to individual subjects is determined by a randomization schedule. Subjects who meet all inclusion criteria and none of the exclusion criteria will be randomized in a 1:1 ratio to either SHP465 6.25 mg or placebo. Randomization will be stratified to ensure approximately 50% of subjects in each age group (6-8 years and 9-12 years), and to facilitate balance of treatment allocation within each age group. The study is not powered to detect within age stratum treatment effects.

The randomization number represents a unique number corresponding to investigational product allocated to the subject, once eligibility has been determined. Individual subject treatment is automatically assigned by the interactive web response system (IWRS).

Investigational product packaging identification numbers, separate from randomization numbers/unique identifiers, may also be assigned to subjects for specific treatment assignment as dictated by the study. In these cases, the same investigational product packing identification number may not be assigned to more than 1 subject.

2.3 **Blinding**

This is a double-blind, placebo-controlled study. All investigational and reference product (SHP465 6.25 mg or placebo) will appear identical to protect the study blind.

Data that may potentially unblind the treatment assignment (i.e., treatment allocation, and investigational product preparation/accountability data) will be handled with special care during the data cleaning and review process. These data will be handled in such a way that, prior to unblinding, any data that may unblind study team personnel will be presented as blinded information or otherwise will not be made available. If applicable, unblinded data may be made available to quality assurance representatives for the purposes of conducting independent drug audits.

The treatment assignment must not be broken during the study except in emergency situations where the identification of the investigational product is required for further treatment of the subject. The investigator should contact the medical monitor as soon as possible after the investigator has been unblinded.

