2.5 Determination of Sample Size

The primary efficacy endpoint is defined as the change from baseline in the Attention-deficit/Hyperactivity Disorder Rating Scale Version 5 (ADHD-RS-5) total score at Visit 6 (Week 4). The baseline ADHD-RS-5 total score is the last value obtained prior to taking the first dose of investigational product, usually at Visit 2.

The null hypothesis is that there is no difference in mean change from baseline at Visit 6 (Week 4) in ADHD-RS-5 total score between SHP465 6.25 mg and placebo, and the alternate hypothesis is that there is a difference in mean change from baseline at Visit 6 (Week 4) in ADHD-RS-5 total score between SHP465 6.25 mg and placebo.

The sample size was estimated for the primary comparison of SHP465 at 6.25 mg with placebo by using nQuery Advisor 7.0. To detect an assumed difference of 11.9 for the change from baseline in the ADHD-RS-5 total score between the SHP465 at 6.25 mg treatment group and the placebo group with the assumed common standard deviation (SD) of 14, 26 completers per group are needed to provide 85% power for a 2-sided t-test with α level of 0.05. This yields a total of 52 subjects (26 on active treatment and 26 on placebo). Taking into account an expected post-randomization dropout rate of 15%, the randomization target is set at 60 subjects in total.

The assumptions of a treatment difference of 11.9 and a standard deviation of 14.0 corresponds to an effect size of 0.85 which is low compared with that in recently completed study (SHP465-305) of children and adolescents aged 6-17 years with ADHD treated with SHP465. The SHP465-305 study yielded an effect size of 0.93 in children aged 6-12 years (101 subjects).

A blinded interim analysis at the late stage of the trial (when approximately 75% of all randomized patients have either completed or discontinued from the study) is needed for a possible sample size increase in case of an underestimated variability postulated at the design stage (see Section 15).

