22.2 Appendix 2 Sample SAS Codes

Mixed Model Repeated Measures (MMRM)

```
Proc mixed /* select derived data set */;
Class trt subjid visit agegp;
Model chg = trt visit agegp trt*visit base base*visit / ddfm=kr;
Repeated visit / subject=subjid type=UN;
/* LSMean, Estimate, and/or LSMestimate statement(s) */
/* Data output or object delivery statement(s) */
Run;
```

Mixed Model Repeated Measures (MMRM) for subgroup analysis

```
Proc mixed /* select derived data set */; Class trt
subjid visit;
Model chg = trt visit trt*visit base base*visit / ddfm=kr; Repeated visit /
subject=subjid type=UN;
by subgroup;
/* LSMean, Estimate, and/or LSMestimate statement(s) */
/* Data output or object delivery statement(s) */
Run;
```

Analysis of Covariance (ANCOVA)

```
Proc glm /* select derived data set */;
Class trt;
Model chg = trt agegp base/alpha=.05;
Lsmeans trt/stderr pdiff;
/* Data output or object delivery statement(s) */
Run;
```

Missing Not at Random (MMNAR) Sensitivity Analysis

Model 1: Placebo Multiple Imputation

```
* Step 1;
proc mi data=unimputed out=discard nimpute=200 seed=309 noprint;
    where treatment=1; * where 1 stands for placebo;
    var baseline chy1-chy4;
    mcmc outest=posteriors; * here we pick up the PLA posteriors;
run;

* 100 posteriors for the placebo, rest for SHP465 6.25 mg;
data posteriors(type=est);
    set posteriors;
```

```
if 1<=_imputation_<=100 then do; * assign placebo posteriors;
              treatment=1;
         end;
        if 100<_imputation_<=200 then do; * assign posteriors to SHP465 6.25 mg;
              treatment=2;
              _imputation_=_imputation_-100;
        end;
 run;
 proc sort data=unimputed;
    by treatment;
 run;
 proc mi data=unimputed out=imputed;
    by treatment;
    var baseline chy1-chy4;
    mcmc inest=posteriors; * here we use the placebo posteriors;
 run;
 * Step 2;
data endpoint;
    set imputed;
    endpoint=chy4;
run;
 proc sort data=endpoint;
    by _imputation_;
 run;
 proc glm data=endpoint;
    by _imputation_;
    class treatment agegp;
    model endpoint = baseline treatment agegp / solution;
    Ismeans treatment;
    estimate 'SHP465 6.25 mg vs placebo' treatment -1 1;
    ods output estimates=est;
 run;
 * Step 3;
 proc sort data=est;
    by label_imputation_;
 run;
 proc mianalyze data=est;
    by label;
    modeleffects estimate;
    stderr stderr;
 run;
```

Protocol SHP465-309

Model 1.

Model 2: Multiple Imputations with Penalties Applied to Dropouts

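### Age group, the randomisation stratum, is missing from the subgroup SAS code and from the CGI-I subgroup model, so text and code specify different models for sex, race and ethnicity

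*SAP*

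**What the plan says.** SAP Section 2.2 makes age group (6-8 and 9-12 years) the stratification factor: "Randomization will be stratified to ensure approximately 50% of subjects in each age group". Section 11.1 and the primary MMRM code in Appendix 2 (Section 22.2) both include it in the model.

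Section 11.7 says the ADHD-RS-5 total score "will be analyzed separately for age group (6-8 years and 9-12 years), sex group (male and female"), and likewise for race and ethnicity. It lists age group among the factors and makes one exception: the factor is dropped when age group itself defines the subgroup.

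For CGI-I, Section 11.7 refers to the primary endpoint's MMRM and then specifies it "with treatment group, visit, and the interaction of treatment group with visit as factors, and baseline CGI-S score used as a covariate", plus the interaction of that covariate with visit. Age group is not in the list, for any subgroup.

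Appendix 2 has a single code block for subgroup MMRMs, run by subgroup. Its model statement is "Model chg = trt visit trt*visit base base*visit / ddfm=kr". The variable agegp is absent from both CLASS and MODEL.

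**The concern.** A programmer who follows the ADHD-RS-5 text for sex, race and ethnicity fits a model with age group. One who follows the code fits a model without it. The SAP gives no rule on which prevails.

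For CGI-I, the reference to the primary method implies age group, but the explicit factor list leaves it out.

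Stratification balances treatment within each age group overall. It does not guarantee that balance among, for example, the girls alone. In a small subgroup, a chance difference in age mix between arms passes into the unadjusted treatment difference. Adjusting for the stratum removes most of this, and the variable is already in the data set. If the discrepancy stays open, the choice of model may be made after the results are known.

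**Working it through.** **1. The specifications side by side.**

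| Place in SAP | Analysis | Age group in model? |
|---|---|---|
| 11.1, text | Primary ADHD-RS-5 | Yes |
| 22.2, primary code | Primary ADHD-RS-5 | Yes (CLASS and MODEL) |
| 11.7, text | ADHD-RS-5 by sex, race, ethnicity | Yes |
| 11.7, text | ADHD-RS-5 by age group | No, by stated exception |
| 11.7, text | CGI-I, all subgroup factors | Not listed |
| 22.2, subgroup code | All subgroup factors | No |

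The code agrees with the ADHD-RS-5 text only for the age-group analysis, where the factor is constant within each fit and must be left out. It disagrees for sex, race and ethnicity. For CGI-I, list and code agree with each other but not with the primary model that the text invokes.

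**2. Cost of restoring the factor.** With four post-baseline visits, the coded subgroup model has 1 (intercept) + 1 (treatment) + 3 (visit) + 3 (treatment by visit) + 1 (baseline) + 3 (baseline by visit) = 12 mean parameters. Age group makes 13. The unstructured covariance has 4 × 5 / 2 = 10 parameters either way.

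**3. Effect of the omission.** Roughly, the shift in an unadjusted subgroup estimate is the difference between arms in the proportion aged 9-12, times the difference in mean outcome between age groups. The documents give neither quantity within subgroups, so no figure can be put on it.

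**4. Precision of the optional between-subgroup contrast.** Inputs from SAP Section 2.5: "To detect an assumed difference of 11.9 for the change from baseline in the ADHD-RS-5 total score", "with the assumed common standard deviation (SD) of 14", and "26 completers per group are needed to provide 85% power for a 2-sided t-test with α level of 0.05".

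- Check on the plan's own figure: SE = 14 × √(2/26) = 3.88; noncentrality = 11.9 / 3.88 = 3.06; 50 df. The noncentral t gives 85.2% power, which reproduces the stated 85%.
- Cell sizes: half of 52 completers in each age group gives 13 per arm. About 25% female (SAP Section 2.1) gives 0.25 × 52 = 13 girls, taken as 7 and 6, and 39 boys, taken as 20 and 19.
- SE of the difference between two subgroup effects = SD × √(sum of 1/n over the four cells), with 52 − 4 = 48 df.
- Sex: 14 × √(1/7 + 1/6 + 1/20 + 1/19) = 9.0. The 95% CI half-width is 18.1 points. Power is 25% if the two effects differ by 11.9.
- Age: 14 × √(4/13) = 7.8. The half-width is 15.6 points. Power is 32% for the same difference.

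For comparison, the simple t-based half-widths within single subgroups are 17.1 points for girls, 9.1 for boys and 11.3 for each age group. These figures use no covariate adjustment. The blinded SD of 13.29 in Section 2.5.1 would narrow them by about 5% (13.29/14 = 0.95).

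**The case against.** Three points can be made for the plan as it stands.

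First, the appendix offers sample code with placeholders. One generic block serves every subgroup factor, including age, where leaving out agegp is right. The reference to the primary method for CGI-I can also be read as bringing age group in. This makes the intent arguable but does not settle it. The ADHD-RS-5 paragraph in the same section names both the factor and its exception, so silence in the CGI-I list is at best ambiguous.

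Second, a reader might infer that separate fits leave only a comparison of significant with non-significant subgroups. The documents do not support that. For the ADHD-RS-5 subgroups, Section 11.7 provides least squares mean differences with 95% CIs and effect sizes, and lists no subgroup p-value. The subgroups within a factor do not overlap, so an approximate difference between effects can be worked out from the reported results. Only a pre-specified contrast is missing.

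Third, no objective concerns differences in effect between subgroups, and Protocol Section 9.9.3 asks only for an estimate within each. Separate fits also avoid assuming a common covariance. This stands: the lack of an interaction model is not an error, and adding one is optional.

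**Conclusion.** The inconsistency is real and minor. For sex, race and ethnicity, the ADHD-RS-5 text and code specify different models, and the CGI-I subgroup model leaves out the stratum despite being presented as the primary method. The omission is correct in the age-group analysis and should stay there.

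A reader might go on to doubt the main conclusions, but nothing supports that. The primary and key secondary MMRMs, the fixed-sequence test and the sample size do not depend on these models. The analyses are labelled exploratory, and Section 2.2 already says the study is not powered within age strata.

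The numerical effect of the omission is unknown. The half-widths of about 18 points (sex) and 16 points (age) describe only the optional contrast. They assume SD 14, 52 completers and the planned age and sex shares. Both exceed the assumed treatment effect of 11.9, so that contrast could be descriptive only. The documents give no race or ethnicity shares, so no contrast figure is given for those factors.

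**What to change.** 1. In the CGI-I paragraph of Section 11.7, list age group as a factor for the sex, race and ethnicity models, and state the same exception for the age-group analysis as in the ADHD-RS-5 paragraph.
2. In Appendix 2, add agegp to the CLASS and MODEL statements of the subgroup block for sex, race and ethnicity. Keep a variant without it for the age-group analysis.
3. Optional: for each subgroup factor, add one FAS model with treatment by visit by subgroup terms and a common unstructured covariance. Report the Week 4 difference in treatment effect between subgroups with its 95% CI, labelled descriptive.

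Items 1 and 2 cost a few words of text, a small code edit and one mean parameter per fit. Item 3 adds one exploratory model per factor on data already collected, assumes the covariance is common across subgroups, and will be imprecise. None needs more subjects or visits. All should be settled before unblinding.

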12. SAFETY ANALYSES

Safety data will be analyzed for the Safety Set. Safety endpoints include the occurrence of TEAEs, vital signs (systolic and diastolic blood pressure, pulse, temperature, and respiration rate), height and weight, ECG results, C-SSRS, PSQ, and CSHQ. For each safety endpoint, the last value collected before the first dose of double-blind investigational product will be used as baseline for all analyses of that safety endpoint. Except for AE data, only post-baseline assessments from Visit 2 (Week 0) up to Visit 6 (Week 4) that were collected on or before 2 days after the last dose of double-blind investigational product will be analyzed. A Final on-Treatment Assessment (FoTA) will be defined as the last valid assessment obtained after Baseline and whilst on investigational product (on or before 2 days after the last dose date).

12.1 Adverse Events

Adverse events will be coded using Version 18.0 of Medical Dictionary for Regulatory Activities (MedDRA).

An AE (classified by preferred term) that occurs during the Treatment period will be considered a TEAE if it has a start date on or after the first dose of double-blind investigational product or if it has a start date before the date of the first dose of double-blind investigational product, but increases in severity on or after the date of the first dose of double-blind investigational product. An AE that occurs after more than 3 days of the last dose of double-blind investigational product will not be counted as a TEAE. If more than 1 AE with the same preferred term is reported before the date of the first dose of double-blind investigational product, then the AE with the greatest severity will be used as the benchmark for comparison to the AEs occurring during the Treatment period under the preferred term.

An overall summary of the number of subjects with TEAEs in each treatment group will be presented, including the number and percentage of subjects with any TEAEs, serious TEAEs, TEAEs related to investigational product, TEAEs leading to drug withdrawal, severe TEAEs and serious TEAEs leading to death.

The number and percentage of subjects reporting TEAEs in each treatment group will be tabulated by system organ class (SOC) and preferred term; by SOC, preferred term, and severity; and by SOC, preferred term, and relationship to investigational product. If more than 1 AE occurs with the same preferred term for the same subject, then the subject will be counted only once for that preferred term using the most severe and most related occurrence for the summarization by severity and by relationship to investigational product.

The incidence of common (≥ 2% of subjects in any treatment group) will be summarized by preferred term and treatment group, sorted in decreasing frequency for subjects on SHP465 6.25 mg, and then for placebo. The incidence of TEAEs, serious TEAEs, and TEAEs leading to withdrawal will be summarized by SOC, preferred term and treatment group, sorted in decreasing frequency for subjects on SHP465 6.25 mg, and then for placebo.

For the Safety Set, listings will be presented for all AEs, TEAEs related to investigational product, TEAEs leading to drug withdrawal, and serious TEAEs.

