8.1.1 Severity Categorization

The severity of AEs must be recorded during the course of the event including the start and stop dates for each change in severity. An event that changes in severity should be captured as a new event. Worsening of pretreatment events, after initiation of investigational product, must be recorded as new AEs (for example, if a subject experiences mild intermittent dyspepsia prior to dosing of investigational product, but the dyspepsia becomes severe and more frequent after first dose of investigational product has been administered, a new AE of severe dyspepsia [with the appropriate date of onset] is recorded on the appropriate CRF).

The medical assessment of severity is determined by using the following definitions:

Mild: A type of AE that is usually transient and may require only minimal treatment or

therapeutic intervention. The event does not generally interfere with usual

activities of daily living.

Moderate: A type of AE that is usually alleviated with specific therapeutic intervention. The

event interferes with usual activities of daily living, causing discomfort but poses

no significant or permanent risk of harm to the research subject.

Page 56

07 September 2017

Severe: A type of AE that interrupts usual activities of daily living, or significantly affects clinical status, or may require intensive therapeutic intervention.

8.1.2 **Relationship Categorization**

A physician/investigator must make the assessment of relationship to investigational product for each AE. The investigator should decide whether, in his or her medical judgment, there is a reasonable possibility that the event may have been caused by the investigational product. If there is no valid reason for suggesting a relationship, then the AE should be classified as "not related". Otherwise, if there is any valid reason, even if undetermined or untested, for suspecting a possible cause-and-effect relationship between the investigational product and the occurrence of the AE, then the AE should be considered "related". The causality assessment must be documented in the source document.

The following additional guidance may be helpful:

Term	Relationship Definition		

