- Summary of duration of TEAE while on study drug: The duration of each event is the number of days from the onset of the TEAE, while on study drug during SHP465 6.25 mg, until the earlier of the end date of the TEAE or the date of last dosing + 3 days (if the date of last dosing is missing, the date of last day on study will be used). TEAEs that either overlap in time, or are adjacent in time will be merged into one TEAE only for the purposes of calculating duration of event. If a subject has multiple TEAEs that

Protocol SHP465-309

are not overlapping or adjacent in time, the durations will be averaged for that subject. Summary statistics are then based on the averaged subject durations. The calculated duration only includes the duration of TEAEs.

- Number and percentage of mild, moderate and severe TEAEs: Overlapping TEAEs with different preferred terms are counted as multiple TEAEs.
- Summary of the number of TEAEs per subject: Overlapping TEAEs with different preferred terms are counted as multiple TEAEs.
- Number and percentage of TEAEs that:
 - Resolved while on study drug
 - Ongoing
 - Dose interrupted
 - Dose withdrawn (and other action categories related to dose)
 - TEAEs leading to discontinuation
 - Number of subjects who discontinued investigational product due to the event

Also, for each of these 3 AEs, the following information will be presented by week:

- Number of subjects in the study
- Number and percentage of subjects with the TEAE
- Number of TEAEs
- Number and percentage of subjects who discontinued due to the TEAE
- Number and percentage of mild, moderate and severe TEAEs. If a subject has more than one TEAE in the same week, then the worst severity is counted.

Where, Week 1 includes TEAEs that start after Visit 2 (Baseline) through Visit 3 (Week 1), Week 2 includes TEAEs that start after Visit 3 (Week 1) through to Visit 4 (Week 2), Week 3 includes TEAEs that start after Visit 4 (Week 2) through to Visit 5 (Week 3), and Week 4 includes TEAEs that start after Visit 5 (Week 3) through to Visit 6 (Week 4).

In addition, for each subject, all occurrences of each of these 3 AEs will be listed separately by treatment group, subject, start date and stop date. The information presented will include: subject, sex, age, race, ethnicity, preferred term/adverse event, start date, stop date, onset day, study visit, last dose date, duration/imputed duration of TEAE (days), SAE, severity, effect on dosing and treatment for AE.

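### Splitting AE records at each severity change inflates event counts for three AEs of interest, and SAP 12.1 leaves open whether a pre-dose event that improves is a TEAE

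*SAP*

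**What the plan says.** Protocol 8.1.1 asks sites to record severity throughout an event, "including the start and stop dates for each change in severity", and then says: "An event that changes in severity should be captured as a new event". It names no direction, so an improvement splits a record just as a worsening does. For events that predate treatment it also says: "Worsening of pretreatment events, after initiation of investigational product, must be recorded as new AEs".

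SAP 12.1 sets its TEAE rule at preferred-term level: "An AE (classified by preferred term) that occurs during the Treatment period" can qualify through either of two limbs. It "will be considered a TEAE if it has a start date on or after the first dose of double-blind investigational product", or it began earlier "but increases in severity on or after the date of the first dose of double-blind investigational product". Events that occur more than 3 days after the last dose are excluded. The same paragraph adds that, when more than one AE of a term was reported before first dose, the most severe of them "will be used as the benchmark for comparison to the AEs occurring during the Treatment period under the preferred term". It does not say what the comparison decides, and it is silent on a single pre-dose AE.

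The SAP 12.1 tables count subjects, once per preferred term, at the worst severity and closest relationship. Event-level summaries appear in SAP 12.1.1 for insomnia, weight decrease and decreased appetite: number of TEAEs, severity split, TEAEs per subject, and counts and percentages by outcome and action. There, overlapping or adjacent TEAEs "will be merged into one TEAE only for the purposes of calculating duration of event". Overlapping TEAEs with different preferred terms count separately; adjacent records of the same term are not addressed.

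Protocol 9.10 defines a TEAE as an AE that begins or worsens between first dose and 3 days after last dose. It plans numbers of events overall, by SOC and by preferred term.

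**The concern.** The recording rule and the counting rules use different units. Sites produce one record per severity level, while a reader of a safety table takes one event to mean one episode. Where the SAP counts records, a child whose insomnia fluctuates looks like a child with several insomnias, and the severity split describes steps within an episode instead of how bad it became.

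The second problem concerns who has a TEAE at all. AEs are collected from consent (Protocol 8.1), through a screening and washout period of up to 32 days (Protocol 3.2), so pre-dose records are foreseeable. If such an event eases after first dose, the milder record carries a post-dose start date. Whether it is a TEAE depends on which part of SAP 12.1 the programmer follows, so two competent programmers could report different incidence from the same data. SAP section 16 places insomnia, and decreased appetite leading to weight loss, under active surveillance by the data monitoring committee, so these are figures that will be read closely.

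**Working it through.** The documents state no figure for this point, so there is none to reproduce. The check applies the written rules to simple histories.

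**1. Splitting of one on-drug episode.** An episode with k severity changes yields k + 1 records under Protocol 8.1.1. Take insomnia that starts mild on day 2, becomes moderate on day 5 and returns to mild on day 9, so k = 2:

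- Records counted: 2 + 1 = 3 TEAEs. Merged into an episode: 1.
- Severity split by record: 2/3 = 67% mild, 1/3 = 33% moderate. By episode: one moderate event.
- Denominator for the outcome and action percentages: 3 instead of 1.
- Weekly lines: TEAEs are assigned by start date, so a severity step in a later week enters the child as having a TEAE in that week too. The weekly severity line takes the worst severity per subject and week, which removes repeats within a week.
- Subject count, day of first onset and merged duration do not change.

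**2. TEAE status of a continuing pre-dose event.** Five invented histories, each one child and one preferred term, were counted in three ways: by the start-date limb alone; by a benchmark reading, in which a post-dose record must exceed the worst pre-dose severity of that term; and by that benchmark with adjacent records collapsed. The benchmark columns assume that it also applies to a single pre-dose AE, which the SAP does not say.

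| History | Start-date limb: events / children | Benchmark: events / children | Benchmark and collapse: episodes |
|---|---|---|---|
| Pre-dose moderate; mild from day 3 | 1 / 1 | 0 / 0 | 0 |
| Pre-dose mild; moderate day 3; mild day 8 | 2 / 1 | 1 / 1 | 1 |
| New mild day 2; moderate day 5; mild day 9 | 3 / 1 | 3 / 1 | 1 |
| Pre-dose severe; moderate day 4; mild day 9 | 2 / 1 | 0 / 0 | 0 |
| New mild day 2, unchanged | 1 / 1 | 1 / 1 | 1 |
| Total | 9 / 5 | 5 / 3 | 3 |

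The third row gives 3 events under both readings of the TEAE definition, so the splitting problem does not depend on that definition. The first and fourth rows show that the choice of reading changes the number of children with a TEAE, from 3 to 5 in this set. Counting a subject once per term does not help there, because the question is whether the subject should be counted at all. The histories show the mechanism and do not estimate its frequency.

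**3. Size per child.** With 60 randomized 1:1, an arm has about 30. One child counted only because a pre-dose event improved adds 1/30 = 3.3 percentage points to that arm's incidence for the term.

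**4. Why the benchmark does not settle it.** In the first row there is one pre-dose record, so the condition of more than one is not met and the benchmark does not apply as written. The start-date limb then applies with no severity test. The second limb has almost no work left, because a worsening already creates a post-dose record under Protocol 8.1.1.

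**The case against.** The strongest reply is that SAP 12.1 classifies AEs by preferred term and names a pre-dose severity benchmark for comparison with treatment-period AEs. That benchmark would have little purpose if every post-dose record qualified automatically. Protocol 9.10 points the same way, since an improving event neither begins nor worsens. This stands as evidence of intent. A reader might infer that improving pre-dose events will be reported as TEAEs; the documents do not support that as settled. They support only that the operative rule is undefined, and that the literal reading yields this result.

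A reader might also infer that AE counts are inflated throughout. They are not: splitting leaves the main SAP 12.1 tables untouched, and the effect is confined to event-level lines for three AEs plus the Protocol 9.10 event numbers, if produced. Three further inferences fail:

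- That the share of resolved events is inflated. Protocol 8.1.3 also offers recovering and not-recovered outcomes, and nothing says which one a site enters when a record closes on a severity change. Only the denominator effect is certain.
- That counts double or triple. That merely restates an assumed k in k + 1, and the documents give no k.
- That SHP465 suffers more. The documents establish no direction, and pre-dose events precede treatment, so randomization gives no reason to expect more of them in one arm.

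Finally, merging for duration only is explicit and prespecified, subject counts stand beside the event counts, and the listings show every occurrence. That limits the harm. It does not make three records of one continuous insomnia three events.

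**Conclusion.** The point holds in two parts. First, under any reading of the TEAE definition, one continuous episode with k severity changes counts as k + 1 events in the number of TEAEs, TEAEs per subject, the overall severity split and the outcome and action denominators for the three AEs. This rests only on sites following Protocol 8.1.1.

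Second, SAP 12.1 does not determine the status of a single pre-dose event that improves after first dose. Read literally it is a TEAE, in conflict with Protocol 9.10, at 3.3 percentage points per such child. That figure assumes an arm of 30 and a child who would not otherwise be counted for that term.

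The total effect in this trial cannot be derived, and neither can its direction between arms. These are descriptive safety summaries; efficacy results and type I error are unaffected. The point deserves correction because it changes reported safety figures and costs very little to settle.

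**What to change.** 1. SAP 12.1: state that a post-dose record continuing, without a gap, a pre-dose AE of the same preferred term is a TEAE only if its severity exceeds the greatest pre-dose severity of that term, including when there is only one pre-dose AE.
2. SAP 12.1.1: for event counts, TEAEs per subject, severity and outcome, collapse adjacent or overlapping records of the same preferred term into one episode, with the worst severity and the last outcome. Keep the rule that overlapping TEAEs with different preferred terms count separately, and leave the duration merge as it is. The duration merge cannot simply be reused, because it is not limited to one preferred term and insomnia pools four.

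If the Protocol 9.10 event numbers are produced, use the same episode rule for them.

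The cost is two SAP sentences and minor extra programming, with no new data. The event-level tables lose the record-level steps, but these remain in the listings. SAP 12.1.1 already plans a review of these preferred terms before database lock, which is a natural place to confirm the rule.
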